## Appendix I. Table of Assessments

| Assessment  | Screening | V1 | V3 | V4 |
|---|-----------|----|----|----|
| Informed Assent/Consent   | X         |    |    |    |
| Demographics  | X         |    |    |    |
| Medical History Questionnaire and Screening   | X         |    |    |    |
| Autism Diagnostic Observation Schedule, 2 nd Edition (ADOS-2) or Autism Diagnostic Interview – Revised (ADI-R) – if needed   | X         |    |    |    |
| Wechsler Abbreviated Scale of Intelligence (WASI-II) – if needed  | X         |    |    |    |
| Medications, Screening  | X         |    |    |    |
| PsyToolkit's Eriksen Flanker and Wisconsin Card Sorting Tasks   |           | X  | X  | X  |
| SCAN-3:A Test for Auditory Processing Disorders in Adolescents and Adults   |           | X  | X  | X  |
| Dynamic Affect Recognition Evaluation (DARE)  |           | X  | X  | X  |
| Behavior Rating Inventory of Executive Function, Second Edition (BRIEF-2)   |           | X  | X  | X  |
| Mind Bender   |           | X  | X  | X  |
| Pediatric Quality of Life Inventory (PedsQL)  |           | X  | X  | X  |
| Brain-Body Center Sensory Scales (BBCSS)  |           | X  | X  | X  |
| Repetitive Behavior Scale - Revised (RBS-R)   |           | X  | X  | X  |
| Social Responsiveness Scale, Second Edition (SRS-2)   |           | X  | X  | X  |
| Social Skills Improvement System - Rating Scales (SSIS-RS)  |           | X  | X  | X  |
| Achenbach System of Empirically Based Assessment (ASEBA) - Age Dependent: Child Behavior Checklist (CBCL - parent report), Youth Self Report Form (YSR), Adult Self-Report (ASR), or Adult Behavior Checklist (ABC) |           | X  | X  | X  |
| Test of Adolescent Social Skills Knowledge (TASSK)  |           | X  | X  | X  |
| Medications, Since Last Visit   |           | X  | X  | X  |
| Adverse Effects   |           | X  | X  | X  |
| Unanticipated Adverse Effects   | As needed |    |    |    |
| Study Exit  | As needed |    |    |    |

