**Measures of Social Cognitive Functioning:** We designed CICADAS to improve sensory processing abnormalities and social cognition in adolescents with ASD independently and to work in conjunction with PEERS to further enhance response to treatment. Our rationale is that many individuals are unable to process accurately information that underlies social and interpersonal cues. Thus, improving social cognition via targeted training of sensory processing abnormalities should confer an advantage to participants using CICADAS in conjunction with PEERS. The ability of CICADAS to prime the brain for PEERS will be measured through a subject-specific improvement in social cognition. Social cognitive functioning will be assessed a number of ways in order to gauge gains in social skills as well as ecological validity of the intervention. One of these measures will be the PEERS-based Test of Adolescent Social Skills Knowledge (TASSK; Laugeson & Frankel, 2006), a 22-item survey that assesses the teen's knowledge about the specific social skills taught during the intervention. The TASSK is comprised of sentence stems and two possible answers. Total scores range from 0 to 22, with higher scores reflecting greater knowledge of the taught social skills. Additionally, we will include the performance-based Dynamic Affective Recognition Evaluation (DARE) test for socioemotional abilities in the participant as well as parent-report measures (SRS-2, SSIS-RS) in our outcome a battery.

The secondary statistical analysis methodology is a linear mixed model approach. First, we will investigate in the ITT population any differences in baseline demographic, characterization, outcomes variables. Any such factors that show trend level significant differences ( $p < 0.1$ ) will be noted and used as covariates in the linear mixed model analysis. We will examine the data from each outcome measure using a linear mixed model with group and time as fixed factors, and covariates as necessary from the baseline analysis. Missing data will be handled with an iterative maximum likelihood procedure to optimally estimate model parameters. The key value for significance will be the group by time interaction factor for the model. Within-group effect sizes (Cohen's  $d$ ) will be computed using the mean change scores for quantitative outcomes (end-of-treatment minus baseline) and the change score SDs.

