With 48 participants fully evaluated, we will not have enough power to detect a treatment augmentation effect ascribable to CICADAS. However, data from this pilot trial will be used to power a pivotal RCT in Phase II, as they will allow to explore whether:

- a) the concurrent delivery of CICADAS and PEERS for 16 weeks (B1-B2) induces greater improvements sensory processing, cognition, symptom reduction, social skills and behaviors, as well as quality of life, compared to CICADAS only (A1-A2) or PEERS + Active Control (C1-C2) – *preliminary efficacy of CICADAS as a treatment enhancer for PEERS*;
- b) The concurrent delivery of CICADAS and PEERS for 16 weeks (B1-B2) induces greater improvements sensory processing, cognition, symptom reduction, social skills and behaviors, as well as quality of life, compared to the sequential delivery of CICADAS and PEERS (A1-A3) – *preliminary testing of CICADAS as enhancer vs primer*;
- c) improvements sensory processing, cognition, symptom reduction, social skills and behaviors, and quality of life induced by the concurrent delivery of CICADAS and PEERS (B1-B2) are sustained after 16 weeks of no contact (B2-B3) – *durability of augmentation effects*.

To verify these experimental hypotheses, we will conduct the analysis based on the pre-intervention (baseline) and post-intervention data. The criterion for statistical significance is  $p < 0.05$ . Results with  $p < 0.1$  will be described as trends.

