#### Calculations from CRFs

The following calculations must be made from CRF data to create the required data tables. These calculations are performed automatically by scripts that operate on the tables from the EDC and produce processed data in new tables.

- **Cognition** *a priori* composite: PsyToolkit's Eriksen Flanker and Wisconsin Card Sorting Tasks, SCAN-3:A Test for Auditory Processing Disorders in Adolescents and Adults, Behavior Rating Inventory of Executive Function, Second Edition (BRIEF-2)
- **Symptoms** *a priori* composite: Child Behavior Checklist (CBCL), Repetitive Behavior Scale - Revised (RBS-R), The Social Responsiveness Scale, Second Edition (SRS-2)
- **Functioning** *a priori* composite: Social Skills Improvement System-Rating Scales (SSIS-RS), Pediatric Quality of Life Inventory (PedsQL)

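### The SAP sets a significance and trend rule over 13 or more secondary efficacy outcomes with no lead outcome, order or adjustment, in a trial it calls preliminary and underpowered

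*SAP*

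**What the plan says.** The relevant text is in the SAP under Secondary Outcome - Preliminary Efficacy and Measures of Social Cognitive Functioning.

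- **Model.** "We will examine the data from each outcome measure using a linear mixed model with group and time as fixed factors", with covariates where baseline differences appear.
- **Key test.** "The key value for significance will be the group by time interaction factor for the model".
- **Hypotheses.** Three are listed, each over sensory processing, cognition, symptoms, social skills and behaviours, and quality of life. Hypothesis a compares Arm B with Arm A and with Arm C at week 16. Hypothesis b compares Arm B's 16-week change with Arm A's 32-week change. Hypothesis c concerns durability within Arm B.
- **Decision rule.** "To verify these experimental hypotheses, we will conduct the analysis based on the pre-intervention (baseline) and post-intervention data". "The criterion for statistical significance is" p<0.05, and results with p<0.1 "will be described as trends".
- **Use.** The SAP says there is not enough power to detect augmentation, but "data from this pilot trial will be used to power a pivotal RCT in Phase II".

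Appendix I of the protocol repeats 13 instruments at V1, V3 and V4 (12 rows, with Flanker and Wisconsin Card Sorting sharing one). The protocol's secondary-outcome paragraph (Intervention Embedded Assessments) adds weekly social gatherings. The SAP's Calculations from CRFs section defines three a priori composites: "The following calculations must be made from CRF data to create the required data tables". It does not rank them above the individual instruments. Neither document names a lead efficacy outcome, a testing order, a gate or a multiplicity adjustment.

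**The concern.** The SAP pairs an exploratory purpose with a confirmatory decision rule. It says the data will let the team explore hypotheses a-c. It then says the analysis will verify them against a significance criterion, and Design and Analysis Populations lists that criterion among the a priori definitions. With many outcomes and several contrasts, one unadjusted threshold gives many chances for a result to be called significant, or a trend, when nothing works. Followed as written, the plan lets the report describe CICADAS as an enhancer of PEERS, or as better concurrent than sequential, on whichever measure crosses a line. These data also feed the planning of Phase II.

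**Working it through.** **Inputs from the documents.** 48 completers in three equal arms gives 48/3 = 16 per arm. Thresholds are 0.05 and 0.10; sidedness is not stated, so I take two-sided. There are 13 repeated instruments, three between-arm contrasts (B vs A and B vs C at week 16; B at week 16 vs A at week 32) and three composites.

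**Assumptions not in the documents.** Equal correlation between outcomes of 0 to 0.7; within-person correlation between visits of 0.6; normal data; no true effects.

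**1. The SAP's own statement on power.** It gives no power figure or error rate, but its concession can be checked. The standardised difference detectable with 80% power at 16 per arm is (1.960 + 0.842) × √(2/16) = 0.99. By normal approximation, power is about 29% for d = 0.5 and 62% for d = 0.8. The concession is right.

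**2. Independent tests.** The chance of at least one false result in k tests is 1 − (1 − α)^k.

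- k = 13, one interaction test each: 1 − 0.95^13 = 48.7%; 1 − 0.90^13 = 74.6%.
- k = 13 × 3 = 39 contrasts: 1 − 0.95^39 = 86.5%, with 39 × 0.05 = 1.95 false results expected. This is too high, because the contrasts share Arm B.
- k = 13, B vs C, favouring B only (half of α): 1 − 0.975^13 = 28.0%; 1 − 0.95^13 = 48.7%.
- k = 3 composites: 1 − 0.95^3 = 14.3%.

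**3. Allowing for correlation.** I simulated three visits under the global null. A three-arm F test on the week 0 to 16 change stands in for the interaction, and two-sample t-tests serve for the contrasts. At 2,500 or more trials per setting, repeat runs differ by up to about two percentage points.

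| Reading of the plan | p<0.05, correlation 0.7 to 0 | p<0.1, correlation 0.7 to 0 | At correlation 0.5 |
|---|---|---|---|
| 13 instruments, interaction only | 26-49% | 42-75% | 34% / 54-55% |
| 13 instruments, three contrasts each | 50-81% | 72-96% | 62-63% / 85% |
| 13 instruments, B vs C, favouring B only | 12-29% | 21-49% | 16-18% / 27-29% |
| Three composites, interaction only | 10-14% | 20-27% | 12-13% / 23-24% |

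Weekly social gatherings, as a fourteenth outcome, raise the upper ends slightly: to 51% and 78% for the interaction, and to 84% and 98% for the contrasts.

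**4. Do the composites shrink the family?** They cover nine instruments: four in Cognition, three in Symptoms and two in Functioning. DARE, TASSK, BBCSS and Mind Bender are in none, yet the SAP singles out DARE and TASSK as social-cognition measures. No sentence limits testing to the composites.

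**The case against.** The strongest reply is that this is a pilot and says so. Feasibility is primary and carries no significance tests. The protocol states that N is not driven by hypothesis testing. The efficacy section is headed preliminary and concedes low power. Formal error control is not essential in such a trial, and one loose verb should not outweigh several explicit limits. This stands as to severity. It does not remove the stated criterion or the trend label, which govern what the report may declare.

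A second reply is that the key test is one interaction per outcome. That also stands in part: on it, the chance of a false result at p<0.05 is about one half at most. But the SAP does not make the interaction a gate for the contrasts, and the trend rule raises the figure to 42-75%.

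Some stronger readings are tempting but unsupported:

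- **A false claim for CICADAS is likely.** The 50-81% counts results in either direction. B vs C isolates CICADAS added to PEERS, and false results favouring B there are 12-29% at p<0.05.
- **Most significant results would be chance.** That depends on how plausible real effects are, which the documents do not quantify.
- **Phase II will be sized from whichever measure stands out.** The SAP says only that the data will be used to power it.
- **The digital assessments add ten more outcomes.** Mind Bender is already among the 13, and the ten are taken only before and after the first period, so they cannot inform Arm A's 32-week change.

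**Conclusion.** The concern holds as an inconsistency between exploratory purpose and decision rule, and is of moderate weight. Under a global null at 16 per arm, at least one false result over 13 instruments has a chance of about 26-49% at p<0.05 and 42-75% at p<0.1 on the interaction. It rises to about 50-81% and 72-96% if the three contrasts are each tested. If only the three composites were tested on the interaction, the chance would be about 10-14% at p<0.05, but the SAP sets no such limit. All ranges rest on assumed correlations and two-sided tests. Multiple scores per instrument, multiple analysis populations and hypothesis c are not counted. The primary feasibility outcomes are unaffected.

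**What to change.** In the SAP paragraph after hypotheses a-c, replace the sentence about verifying the hypotheses and the p<0.05 / p<0.1 rule with wording such as: All secondary efficacy analyses are exploratory. Between-arm estimates with 95% confidence intervals are reported for every outcome. P-values are nominal and unadjusted, and no outcome is declared significant or a trend. Amend the mention of a significance criterion in Design and Analysis Populations to match.

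If the sponsor keeps any significance statement, limit it to a small set named before unblinding, for example the three a priori composites with Holm's procedure, and leave individual instruments descriptive. Adjusting everything is not workable: Bonferroni over 13 outcomes (0.05/13 = 0.0038) leaves about 7% power for d = 0.5 and 27% for d = 0.8.

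The cost is SAP wording only, with no new data, visits or participants. The downside is that isolated p<0.05 or p<0.1 results can no longer be called significant or trends.

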#### Calculations from CRFs

The following calculations must be made from CRF data to create the required data tables. These calculations are performed automatically by scripts that operate on the tables from the EDC and produce processed data in new tables.

- **Cognition** *a priori* composite: PsyToolkit's Eriksen Flanker and Wisconsin Card Sorting Tasks, SCAN-3:A Test for Auditory Processing Disorders in Adolescents and Adults, Behavior Rating Inventory of Executive Function, Second Edition (BRIEF-2)
- **Symptoms** *a priori* composite: Child Behavior Checklist (CBCL), Repetitive Behavior Scale - Revised (RBS-R), The Social Responsiveness Scale, Second Edition (SRS-2)
- **Functioning** *a priori* composite: Social Skills Improvement System-Rating Scales (SSIS-RS), Pediatric Quality of Life Inventory (PedsQL)

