### ***Cognitive Function***

At *Screening Visit (V0)*: Cognitive status will be determined using the WASI-II or a comparable measure in their medical/clinical records. An IQ > 70 is required to enroll in the study. Adult participants will undergo an additional cognitive assessment, the UBACC. Participants must score within the normal range; participants who cannot pass the UBACC will not be eligible for enrollment.

For *Baseline (V1)*, *Mid-Intervention (V3)* and *Post-Intervention (V4)* Visits: We will assess cognition directly by administering the Behavior Rating Inventory of Executive Function, Second Edition (BRIEF-2), Mind Bender, and PsyToolkit's Eriksen Flanker and Wisconsin Card Sorting Tasks.

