### ***Sensory Processing***

We will assess sensory processing by administering the SCAN-3:A Tests for Auditory Processing Disorders in Adolescents and Adults and the Brain-Body Center Sensory Scales (BBCSS).

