### ***Intervention Embedded Assessments***

All participants, regardless of treatment group, will complete the ten sensory processing assessments before and after the first intervention period.

**The primary outcome** measures, including digital assessment completion rate, NB-SCT program adherence, usability ratings, reported adverse effects, and overall program completion rate will be used to assess feasibility, acceptability and usability of CICADAS app.

**Secondary outcomes** measures include baseline, mid-intervention, and post-intervention assessments as well as the weekly number of initiated or reciprocated social gatherings related to or in addition to PEERS assigned social activities.

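### The SAP scores SCAN-3:A in the Cognition composite, although the protocol classes it as sensory processing and the SAP hypotheses keep the two domains apart

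*SAP*

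**What the plan says.** The SAP, under Calculations from CRFs, defines three a priori composites: Cognition, Symptoms and Functioning. Cognition consists of the PsyToolkit Flanker and Wisconsin Card Sorting tasks, then "SCAN-3:A Test for Auditory Processing Disorders in Adolescents and Adults, Behavior Rating Inventory of Executive Function, Second Edition (BRIEF-2"). No weights, standardisation or scoring direction are given. There is no sensory-processing composite, and BBCSS is in none of the three.

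The protocol classifies the measures differently. Its Sensory Processing section reads: "We will assess sensory processing by administering the SCAN-3:A Tests for Auditory Processing Disorders in Adolescents and Adults and the Brain-Body Center Sensory Scales (BBCSS"). Its Cognitive Function section names the measures for V1, V3 and V4 as "Behavior Rating Inventory of Executive Function, Second Edition (BRIEF-2), Mind Bender, and PsyToolkit's Eriksen Flanker and Wisconsin Card Sorting Tasks"; SCAN-3:A is not among them.

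The SAP's own hypotheses keep the domains apart. Hypotheses (a) and (b) ask whether concurrent delivery "induces greater improvements sensory processing, cognition, symptom reduction, social skills and behaviors, as well as quality of life", and (c) lists the same domains for durability.

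Two further provisions bear on the point. The SAP fits a linear mixed model to each outcome measure. The protocol, under Intervention Embedded Assessments, adds app-based sensory tests: "All participants, regardless of treatment group, will complete the ten sensory processing assessments before and after the first intervention period".

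**The concern.** In this trial sensory processing is the thing being trained, and the other domains are where benefit is hoped to follow. A summary labelled Cognition that contains a measure of the training target cannot by itself separate the two.

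The comparison most exposed is Arm B against Arm C. The protocol's CICADAS exercise list includes auditory tasks (In the Know, Auditory Ace, Say What?, Voice Choice). The Active Control consists of casual video games, with visual given as the matched modality. An arm difference on an auditory-processing test is therefore plausible without any difference on Flanker, Wisconsin Card Sorting or BRIEF-2, and the composite would record part of it as cognitive. Conversely, if cognition improves and SCAN-3:A does not, the composite understates the cognitive gain.

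What is at stake is how a secondary result is read: evidence that the target was engaged, or evidence of transfer to cognition.

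**Working it through.** **Step 1: classification.**

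| Measure | Protocol domain | SAP composite |
|---|---|---|
| Flanker, Wisconsin Card Sorting | Cognitive Function | Cognition |
| BRIEF-2 | Cognitive Function | Cognition |
| Mind Bender | Cognitive Function | none |
| SCAN-3:A | Sensory Processing | Cognition |
| BBCSS | Sensory Processing | none |

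SCAN-3:A is the only measure in the Cognition composite that the protocol assigns to another domain. Appendix I of the protocol schedules every measure in the table at V1, V3 and V4.

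**Step 2: carry-over of a SCAN-only effect.** The plan gives no composite formula and no figure to reproduce, so the following are assumptions: an equal-weight mean of k unit-variance z-scores, common correlation r from 0.1 to 0.5, and k = 4 (Flanker, Wisconsin, SCAN-3:A, BRIEF-2) or k = 3 (PsyToolkit counted once).

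The SD of the mean is sqrt((1 + (k−1)r)/k). If SCAN-3:A alone shifts by d, the mean shifts by d/k, so

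composite effect = (d/k) / sqrt((1 + (k−1)r)/k) = d / sqrt(k + k(k−1)r).

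| k | r = 0.1 | r = 0.3 | r = 0.5 |
|---|---|---|---|
| 4 | d/sqrt(5.2) = 0.439d | d/sqrt(7.6) = 0.363d | d/sqrt(10) = 0.316d |
| 3 | d/sqrt(3.6) = 0.527d | d/sqrt(4.8) = 0.456d | d/sqrt(6) = 0.408d |

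Take d = 0.8 SD, an illustrative value that is not in the documents. The composite then shows between 0.8 × 0.316 = 0.25 SD and 0.8 × 0.527 = 0.42 SD, with no change in any measure the protocol calls cognitive.

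**Step 3: how often that would reach p < 0.05.** Inputs are 16 completers per arm (protocol, General Study Design) and the SAP's 0.05 criterion, taken as two-sided because sidedness is not stated. By the normal approximation, power = Φ(effect × sqrt(16/2) − 1.96).

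- SCAN-3:A alone: Φ(0.8 × 2.828 − 1.96) = Φ(0.30) = 62%.
- Composite, lowest case: Φ(0.253 × 2.828 − 1.96) = Φ(−1.24) = 11%.
- Composite, highest case: Φ(0.422 × 2.828 − 1.96) = Φ(−0.77) = 22%.

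The composite thus mislabels part of a sensory gain and also makes that gain harder to detect.

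**Step 4: dilution the other way.** Suppose all k−1 cognitive components gain d and SCAN-3:A does not move.

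- With SCAN-3:A included, the effect is ((k−1)/k)d / sqrt((1 + (k−1)r)/k).
- Without it, the effect is d / sqrt((1 + (k−2)r)/(k−1)).
- k = 4, r = 0.1: 1.316d against 1.581d, ratio 0.83.
- k = 3, r = 0.5: 0.816d against 1.155d, ratio 0.71.

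These two cases are the extremes of the grid, so the composite would keep about 0.71 to 0.83 of the effect seen without SCAN-3:A.

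**The case against.** The strongest reply is that little depends on these composites. The SAP models each outcome measure, so SCAN-3:A, BBCSS, Flanker, Wisconsin Card Sorting and BRIEF-2 can each be read alone. In the illustration the single-measure analysis is also the one more likely to show the gain. A reader might infer that a sensory gain would be hidden, or reported only as a cognitive one. The per-measure models rule that out, and this part of the reply stands.

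A reader might also infer that the composites will supply effect sizes for Phase II. The SAP says that data from this trial will power that study; it does not say the composites will. They appear as derivations for data tables, and no hypothesis is tied to them.

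Nor does the composite contaminate the priming question. The SAP measures priming through social cognition and names TASSK, DARE, SRS-2 and SSIS-RS, none of which is in Cognition.

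For the first 16 weeks, the ten app assessments give further evidence on target engagement in all arms. They stop after that period, so they do not serve the week-32 parts of (b) and (c); SCAN-3:A and BBCSS do.

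Lack of a sensory composite is not an error in itself, since TASSK and DARE are in no composite either. Domain labels are also partly a matter of judgement: the protocol treats Mind Bender as a cognition measure in one place and as a sensory assessment in another. A purely sensory gain is an extreme case as well, because some of the auditory exercises are memory and prosody tasks.

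What the reply does not answer is the mismatch. An a priori definition departs from the protocol's classification and from the SAP's own hypotheses, and no reason is given.

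**Conclusion.** The inconsistency stands on the text alone: SCAN-3:A is a sensory measure in the protocol and a cognition component in the SAP, while the SAP hypotheses treat the two domains as separate.

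Its size is conditional. Under the assumed equal weights, three or four components and correlation 0.1 to 0.5, roughly 0.3 to 0.5 of a SCAN-only effect would show up as Cognition. Other weights would change that figure.

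The consequence is confined to the label and interpretation of one composite among secondary, exploratory outcomes, in a trial whose SAP concedes low power for an augmentation effect. The primary feasibility outcomes are untouched. The documents do not support a claim that the sensory result is concealed or that Phase II planning rests on this composite. The point merits correction because the definition is pre-specified and the repair is simple.

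**What to change.** Before data are analysed, amend Calculations from CRFs in the SAP as follows:

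- Remove SCAN-3:A from the Cognition composite, leaving Flanker, Wisconsin Card Sorting and BRIEF-2.
- Report SCAN-3:A with BBCSS as a pre-specified sensory-processing domain, and use it for the sensory part of hypotheses (a) to (c).
- In the same edit, state how each composite is formed (standardisation, weights, scoring direction), and say whether leaving Mind Bender out of Cognition is intended.

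If the sponsor prefers to keep SCAN-3:A under Cognition, the SAP should give the reason and the protocol's domain lists should be brought into line.

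The cost is SAP wording and a script edit. No new data are needed, because both sensory measures are already scheduled at V1, V3 and V4. The small downside is one more exploratory summary to report. Made after results are known, the same change would be a post hoc redefinition.
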